Atrophy in the Entorhinal cortex (ERC) and Hippocampus (HPC), measured on MRI scans, predicts future cognitive decline and conversion to AD among individuals with Mild Cognitive Impairment (MCI). Severity of MTA, assessed with MRI scans, is strongly associated with severity of medial temporal lobe degenerative pathology, especially the severity of neurofibrillary pathology, at autopsy.

HYPOTHESIS 3. Leukine[®] treatment in adults with mild-to-moderate AD will reverse or stop the progression of MTA.

EXPLORATORY AIM 1. To assess whether Leukine[®] treatment will improve specific cognitive domains in mild-to-moderate AD patients.

A battery of cognitive tests will be performed at baseline Day 1 and at approximately 15, 45, and 90 days after initiation of Leukine[®] treatment to determine whether any AD features reverse during or after Leukine[®] treatment compared to subjects receiving placebo. Secondary cognitive domain tests will include the ADCS-ADL (Alzheimer's Disease Cooperative Study Activities of Daily Living Inventory), Trail making tests (TRAILS) A, TRAILS B, Clinical Dementia Rating (CDR), and the Mohs Cancellation Task.

EXPLORATORY HYPOTHESIS 1. Leukine[®] treatment in adults with mild-to-moderate AD will improve specific cognitive domains as measured by the ADCS-ADL, TRAILS A,

TRAILS B, CDR, and the Mohs Cancellation Task.

EXPLORATORY AIM 2. To examine the effects of Leukine[®] treatment in mild-to-moderate AD patients on biomarkers associated with AD .

Biomarkers from peripheral blood collection include various forms of the hallmark proteins that form amyloid plaques in AD (i.e. amyloid-beta [A β] peptides), as well as other proteins which levels are known to be altered in AD (hyper-phosphorylated Tau and various inflammation-associated cytokines and chemokines).

EXPLORATORY HYPOTHESIS 2. Leukine[®] treatment in adults with mild-to-moderate AD will induce changes in blood biomarkers toward published control levels.

EXPLORATORY AIM 3. To determine if Leukine[®] treatment will change amyloid load in mild-to-moderate AD patients.

Amyloid PET scans will be performed using Pittsburgh Compound B (¹¹C-PiB), produced at the UCD-Anschutz Medical Campus (AMC) cyclotron laboratory, which allows for amyloid-beta neuritic plaque density imaging, and will be used to test the hypothesis that Leukine[®] treatment of mild-to-moderate AD subjects reduces cerebral amyloid load.

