EXPLORATORY HYPOTHESIS 3. Leukine[®] treatment in adults with mild-to-moderate AD will change amyloid load.

BACKGROUND AND RESEARCH RATIONALE:

Alzheimer's Disease (AD) is a major cause of death and disability in the elderly, affecting about 12% of those over age 65 and about 40-50% of those over age 85. Although treatments slowing the course of the disease, such as cholinesterase inhibitors or a glutamate receptor agonist are available, their benefits are transient, are only effective for about half of the patients that take them, and they do not attack the etiology of the AD pathogenic pathway. It is therefore imperative that new pharmacological interventions be developed that can prevent or reverse the disease and the associated cognitive decline. Most treatments that are currently under investigation are designed to attack the formation of the A β peptide or its polymerization into neurotoxic oligomers/fibrils. Following encouraging results in animals, human trials have thus far not been very successful. Evidently a completely new approach may be necessary.

Amyloid deposition and cognitive decline in transgenic animals, perhaps because it develops over a relatively short period of time and in the absence of clear neuronal cell death, is fundamentally different from that which leads to AD in humans, and this concern always overshadows the use of animal models for developing AD therapies. We therefore sought a new approach that would identify a new mechanism that would provide protection against AD. Our investigation is based on the epidemiological evidence that the vast majority of people with Rheumatoid arthritis do not tend to develop onset of AD.

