- Should the potential subject have a screening blood pressure (BP) of more than 150 systolic or 95 diastolic, they will need to be under the care of a primary care provider for management of hypertension.
- The BP will have been well-controlled on a stable regimen for at least two months prior to study entry.
- The screening BP will be no greater than 160 systolic or 95 diastolic. (This limit will apply to all and any BP measurements during the screening process.)

Management Criteria during the treatment phase of the study:

- Should blood pressure rise above 165 systolic or 95 diastolic, the patient will be removed from the study.

- The subject’s hypertensive regimen may be adjusted by the primary care provider during the study as needed.

Sample size considerations:

Due to the well documented safety history of Leukine® ([1], attached as Appendix D) combined with additional patient information from the USF site, we believe that a sample size of 20 patients per research arm is adequate to assess our Primary Endpoint of measuring safety. Although the Moffitt BMT study was not specifically designed to distinguish the cognition of patients receiving GM-CSF plus G-CSF from those receiving G-CSF alone, it was possible to glean conclusions about the cognitive benefit of GM-CSF or G-CSF treatment. The study found highly significant improvement (p<0.01) in the scores of 19 patients receiving GM-CSF plus G-CSF, compared to patients receiving only G-CSF.

A Power analysis showed the following results:

Here is a table of the sample size needed per group with alpha at .20 and power at .60 for independent samples t tests:

Effect size	1 tailed test	2 tailed test
.3 - small	27	53
.5 - medium	10	20
.8 - large	4	8
1.22 – observed from BMT	3	4

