Primary Endpoint: Generally, descriptive statistics will be utilized to examine safety of participants who received Leukine® injections compared to placebo injections. Safety will be assessed by measuring the toxicity grades of AE’s. These toxicity grades have been standardized by the

National Cancer Institute (NCI) Common Toxicity Criteria for Adverse Events (CTCAE Version 4.03 attached as Appendix E). Differences in toxicity grades will be compared between treatments using a Wilcoxon test for ordered outcome.

Secondary Endpoint and Exploratory Aim 1: Neuropsychological assessments will be graded and scored using the standardized scoring methods associated with each of the neuropsychological tests. Our primary measures for cognitive assessments will be based on the participants' MMSE total score and ADAS-cog total scores. All other neuropsychometry tests will be used secondarily to examine changes in specific cognitive domains. Due to the multitude of both the neuropsychometry tests and the different time points these tests are administered, a Bonferroi correction method will be used to counteract the problem of multiple comparisons.

Tertiary Endpoint: Medial Temporal Lobe Atrophy (MTA) will be assessed using an automated rating system to grade the severity of atrophy in the entire medial temporal region will be employed using the FreeSurfer software automated rating system of individual medial temporal structures, i.e., the Hippocampus (HPC), Entorhinal cortex (ERC) and Perirhinal cortex (PRC), which are specific regions of interest (ROI) in AD pathogenesis. FreeSurfer automatically computes cortical reconstruction and volumetric segmentation, including segmentation of the subcortical white matter and deep gray matter volumetric structures [34] and parcellation of the cortical surface [35] according to a previously published parcellation scheme [36]. This labels cortical sulci and gyri, and thickness values are calculated in the ROIs.

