Exploratory Aim 3: Amyloid PET scans will be performed using Pittsburgh Compound B (¹¹C-PiB), produced at UCD-AMC, which allows for amyloid-beta neuritic plaque density imaging, and will be used to test the hypothesis that Leukine® treatment of mild-to-moderate AD subjects reduces cerebral amyloid load. ¹¹C-PiB PET scans will be performed at screening and at the first follow-up visit (+/- 7 days depending upon scheduling availability). For quantification of the brain amyloid load, assessments will evaluate the screening ¹¹C-PiB scan before the baseline visit and another ¹¹C-PiB scan within +/- 7 days of the first follow-up visit after the end of treatment with Leukine® or placebo. The change from the screening ¹¹C-PiB scan's SUVR to follow-up SUVR will be analyzed by a contracted central reading facility (i.e., BioClinica, a specialty clinical trial services provider) using the subject's MRI to reduce white matter contamination, thereby increasing the SUVR signal change by eliminating counts in the region that do not change (white matter). The ¹¹C-PiB PET scans and accompanying MRI scans will be stripped of any personal identifying information, containing only the trial's randomized subject ID number and date. Data will be compared using parametric (SPM) and non-parametric (SnPM) statistical methods with family-wise error (FWE) and false discovery rate (FDR) corrections. Comparisons of SUVRs will be made between the first and second PET for each individual study participant. These differences will then be compared between placebo and treatments groups to

determine if Leukine[®] treatment changes amyloid load. The results of the ¹¹C-PiB PET quantitative analyses will not be used to make any treatment decisions.

Important Note: Full-dose data from the two sites will be combined and analyzed together for both safety and cognitive outcomes. Also, other statistical tests that may be utilized include: independent t-tests to examine differences between means; the Chi-square test to assess association between variables; and logistical regression to calculate the ratio of the odds of an event occurring in one group compared to another group.

Dosage:

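### Exploratory Aim 3 does not say which PET result answers the amyloid hypothesis: the SPM/SnPM results are unranked, the SUVR comparison is under-specified, and the direction is worded two ways

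*Combined protocol and SAP*

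**What the plan says.** In the combined protocol and SAP, the Data Analysis Plan entry for Exploratory Aim 3 has three analytic elements.

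- Image statistics: "Data will be compared using parametric (SPM) and non-parametric (SnPM) statistical methods with family-wise error (FWE) and false discovery rate (FDR) corrections".
- Within participants: "Comparisons of SUVRs will be made between the first and second PET for each individual study participant".
- Between arms: "These differences will then be compared between placebo and treatments groups to" establish whether treatment changes amyloid load.

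No sentence ranks these. The entry says a contracted central reader will derive the change from screening to follow-up SUVR, using MRI to limit white-matter contamination. It names no target region, reference region, test, significance level or side.

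The direction is worded in two ways. The descriptive sentence about the scans, which stands both under Specific Aims and in the Data Analysis Plan, tests whether "treatment of mild-to-moderate AD subjects reduces cerebral amyloid load". Exploratory Hypothesis 3 says that "treatment in adults with mild-to-moderate AD will change amyloid load". The formal statement of Exploratory Aim 3 and the closing SUVR sentence also speak of change.

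Two nearby statements do not settle the matter. In the entry for the cognitive endpoints, "a Bonferroi correction method will be used to counteract the problem of multiple comparisons", but that covers the neuropsychological tests and their time points only. The note that ends the Data Analysis Plan leaves the list open: "other statistical tests that may be utilized include: independent t-tests to examine differences between means".

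**The concern.** FWE and FDR corrections control error across voxels inside one map. They do not cover a later choice between SPM and SnPM, between the two corrections, or between a map and the SUVR comparison. The two corrections also support different statements: FWE limits the chance of any false voxel, and FDR limits the expected share of false voxels among those declared. They are not interchangeable answers to one hypothesis.

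If the lead result is picked after the scans are read, its nominal error rate no longer describes the claim. The same holds if the side of the test is picked then. At stake is how far a reported amyloid effect can be believed. The Introductory Statement gives determining such an effect as a reason for adding PET.

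**Working it through.** **1. Number of results.** Two methods times two corrections gives 2 x 2 = 4 map results, and the SUVR comparison makes 5. The four are inferred by crossing; the plan does not list four outputs.

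**2. Significance level.** There is no PET sample size, power or alpha to reproduce. The only stated alpha is in Sample size considerations, for cognition: "sample size needed per group with alpha at .20 and power at .60 for independent samples t tests". Exact noncentral-t calculation gives 27/53, 10/20, 4/8 and 2/4 (one-/two-tailed), against the printed 27/53, 10/20, 4/8 and 3/4. The table reproduces except for one cell, and it says nothing about PET. An alpha of 0.05 per PET analysis is therefore assumed below.

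**3. Limits for any of five at 0.05.** Full dependence gives 5%. Independence gives 1 - 0.95^5 = 22.6%. The sum bound is 5 x 0.05 = 25%. All five come from the same scans, so the independence figure cannot be the actual rate, and simulation is needed.

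**4. Simulation with no treatment effect, 10 per arm, 1,000 runs per row.**

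| Field | Setting | Any of the four maps | Any of the five |
|---|---|---|---|
| 12 x 12 x 12 grid, 300 permutations | FWHM 3 voxels | - | 10.1% |
| 12 x 12 x 12 grid, 300 permutations | FWHM 6 voxels | - | 8.3% |
| 300 smoothed voxels, 999 permutations | shared variance 0 | 6.1% | 9.5% |
| 300 smoothed voxels, 999 permutations | shared variance 0.3 | 5.2% | 9.4% |
| 300 smoothed voxels, 999 permutations | shared variance 0.7 | 4.5% | 6.5% |

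In the 300-voxel runs all five tests are two-sided, SPM-FWE is represented by Bonferroni, SnPM-FWE by the permutation maximum, and FDR by Benjamini-Hochberg. The SUVR comparison is a t test on mean change. Monte Carlo error at 8% is sqrt(0.08 x 0.92 / 1000) = 0.9 percentage points. The range is roughly 6.5-10%.

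In these 300-voxel runs, choosing among the four maps adds little (4.5-6.1%). Most of the excess comes from having a map and the SUVR comparison as alternatives. A positive here is a result in either direction, so these are not rates of false benefit claims.

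**5. Side of the test.** A two-sided 0.05 test puts 0.05 / 2 = 2.5% in the reduction tail. A one-sided 0.05 test for reduction puts 5% there. Choosing the one-sided test afterwards moves false claims of reduction from 2.5% to 5%.

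**6. Scan pairs.** The Introductory Statement adds PET for the remaining two cohorts, 10 Leukine and 10 placebo. Its update section reports a further cohort of 10 completed since that amendment, 30 participants in total, before Amyvid is replaced by PiB. With 40 planned, 40 - 30 = 10 remain, about 5 per arm on PiB. So 10 per arm is reached only by combining two tracers. The current analysis entry mentions PiB alone and does not say what happens to the Amyvid pairs.

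**The case against.** The strongest reply is that the plan does have a deciding comparison. The closing SUVR sentence states its purpose in almost the words of the aim. The entry can also be read as one analysis, with SPM/SnPM as the tools, SUVR change as the data and placebo versus treatment as the contrast. Much of this stands, and a reader who inferred that there is no candidate deciding test would go too far. What remains is that the sentence is not ranked above the maps and lacks a test, region, alpha and side. On the single-analysis reading, the methods and corrections are still unranked.

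A reader might also infer two rival hypotheses. The documents do not support that. The formal aim, the formal hypothesis and the closing sentence agree on *change*; *reduces* occurs only in the repeated descriptive sentence. No one-sided PET test is stated anywhere.

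Two larger figures are tempting. The 22.6% needs independent results, which the same scans cannot give. For the choice of side, 5% + 2.5% = 7.5% is arithmetically right, but the 2.5% consists of apparent amyloid increases, so it is not a rate of false favourable claims.

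Finally, this is an exploratory aim of a pilot with a safety primary endpoint, and quantitative PET results guide no treatment decision. The Introductory Statement stresses learning whether amyloid load is affected, and whether safely, but as the rationale for the Amyvid revision; it promises no confirmatory test. That stands and limits the consequence to reporting.

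**Conclusion.** The concern holds as a specification gap of moderate size. The plan does not say which PET result answers Exploratory Hypothesis 3, leaves its most natural answer (the between-arm SUVR comparison) without the details needed to run it, and words the direction inconsistently. With 10 per arm and an assumed 5% per analysis, taking any positive result gives roughly 6.5-10% false positives. At the low end this is hardly separable from 5%, given the simulation error. Choosing the side afterwards doubles false claims of reduction, from 2.5% to 5%.

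These figures rest on the assumed alpha, the assumed image smoothness and the count of five results. They also ignore the tracer change. About 5 per arm, the likely number on PiB alone, was not simulated. Patient management is not affected. The change should be made because it is cheap and can be settled before the remaining scans are analysed.

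**What to change.** In the Data Analysis Plan, Exploratory Aim 3:

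1. Name the between-arm SUVR comparison as the one deciding test: ANCOVA of follow-up SUVR on arm with screening SUVR as covariate, in one pre-stated cortical composite with one pre-stated reference region. Make it two-sided at a stated alpha, and report the estimate with its 95% CI.
2. Include only participants whose two scans used the same tracer. Account for tracer (Amyvid or PiB) by putting SUVR on a common scale, or by standardising within tracer and adding a tracer term. Raw SUVRs from two tracers should not be pooled in one unadjusted model.
3. Replace *reduces* with *changes* in the descriptive sentence, both under Specific Aims and in the Data Analysis Plan.
4. Keep one pre-named voxelwise method and correction as supportive, for example SnPM with FWE, and report it whatever it shows.

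ANCOVA and SnPM with FWE are reasonable choices, not the only ones; the essential step is to fix one analysis in advance.

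The cost is a short text change in an amendment that already revises the PET section, plus agreement with the central reader on regions and tracer scaling. No new scans or visits are needed. A favourable voxelwise map alone could no longer be reported as confirming the hypothesis. The covariate and tracer term cost degrees of freedom: with 20 participants, from 20 - 2 = 18 for a two-sample t test to 20 - 4 = 16.

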Effects of Leukine[®] on mobilization of white blood cells will be determined by CBC with differential at screening, baseline Day 1 and on days 4, 6, 9, 11 and 15 of the treatment schedule (i.e. placebo or Leukine[®] at 250 mcg /m²/day/SC for 5 days/ week for three weeks), and at the 45 and 90 day follow-up visits. Vital signs, injection site review, and adverse event monitoring will be performed at each treatment visit. Complete metabolic panels (CMP) will be performed at screen, and on days 4, 9, 15, 45, and 90 days after initiation of GM-CSF treatment (Table 1 below summarizes the time-table of procedures for the entire study). The follow up MRI at the end of the treatment phase will provide information on any adverse changes in the brain, such as vasogenic edema and microhemorrhage. The DSMB will review all available data after each group of 5 Leukine[®]-treated and 5 placebo subjects have finished the treatment phase and determine whether the remainder of the subjects (5 Leukine[®]-treated and 5 placebo) will continue to receive the same full recommended dose (250 mcg/m²/day/SC).

HYPOTHESIS 1. Recombinant human GM-CSF, Leukine[®], will be tolerated by, and safe to use in mild-to-moderate AD patients.

SPECIFIC AIM 2. To test the hypothesis that Leukine[®] treatment will improve cognition in mild-to-moderate AD patients (*Secondary Endpoint*).

A battery of cognitive tests will be performed at baseline and at approximately 15, 45, and 90 days after initiation of Leukine[®] treatment to determine whether any AD features reverse during or after Leukine[®] treatment compared to subjects receiving placebo. Primary cognitive tests will include the Mini Mental State Examination (MMSE) and the ADAS-cog (Alzheimer's Disease Assessment Scale-cognitive subscale).

HYPOTHESIS 2. Leukine[®] treatment in adults with mild-to-moderate AD will improve cognition as measured primarily by MMSE total score and ADAS-cog total score.

SPECIFIC AIM 3. To investigate whether Leukine[®] treatment has an effect on Medial Temporal Lobe Atrophy (MTA) in mild-to-moderate AD patients (*Tertiary Endpoint*).

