A summary of all study events are presented in Table 1. All interviews with subjects and potential subjects will be carried out in a private room. At the initial visit (screen), after informed consent is obtained, the MMSE is performed. If the subject qualifies on the MMSE entry criteria then vital signs are recorded, an ECG and a physical exam are performed, and 8 ml of blood is drawn for a CBC with differential, and a complete metabolic panel (CMP). A brain MRI will also be done during the screening period to exclude other causes of dementia and to assess for Medial Temporal Lobe Atrophy (MTA). Also, the first positron emission tomography (PET) scan, using ¹¹C-PiB, will be performed during the screening period to assess evidence of cerebral amyloid load. If the PET scan is performed on the same day as the MRI scan, the PET scan will be performed after the MRI scan. A qualitative read of the ¹¹C-PiB PET scan will be made to determine evidence of β -amyloid neuritic plaques. For women enrolled, who feel that there is a chance they may be pregnant, a pregnancy test will be administered. Clinically, if the patient cannot name their last menstrual period or is uncertain whether they are pregnant or not, a urine dipstick test is performed. The creatinine level from the CMP will also

be used to assess the Glomerular Filtration Rate (GFR). Also a list of all patient medications will be recorded. Patients will have to meet the inclusion/exclusion criteria (stability on AD medications for 2 months prior to screen and all other meds must be stable 30 days prior to screen). Particular caution will be paid to individuals taking Lithium or corticosteroids, but they will not be excluded from the study.

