Once the results are available, if the subject continues to meet entrance criteria they will return for their baseline Day 1 (randomization) visit. This visit takes place about 1 to 4 weeks after the screen visit. At this visit, vital signs are recorded, 33 ml of blood will be drawn for a CBC with differential, a complete metabolic panel (CMP), and for biomarker assays (for example, GM-CSF, IFN- γ , IL-1 β , IL-2, IL-6, IL-8, IL-10, IL-12p70, TNF- α , Eotaxin, IP-10, MCP-1, MCP-4, MIP-1 β , TARC, P-Tau, Total Tau, and A β species), and tests of cognition, such as the MMSE, ADAS-cog, the ADCS-ADL scale, Trails A, Trails B, CDR, and the Mohs Cancellation task, are administered. The test article will then be delivered by the unblinded pharmacist, administered subcutaneously by the (blinded) study nurse or clinician, and the subject then goes home.

Subsequent injections will also be administered at the clinic. About 4 ml of blood will be drawn for CBC plus differential approximately every three days during the treatment phase to monitor for leukocytosis (see safety monitoring plan), and an additional 4 ml of blood will be drawn for CMPs once every week of the treatment phase. Vital signs, injection site review, and adverse events will be recorded at each visit. At the last treatment visit approximately three weeks later, we will record vitals, perform a physical exam, review for adverse events, administer cognitive tests and draw 33 ml blood for a CBC with differential, a CMP, and biomarker assays. A brain MRI will be done for comparison with the initial screen MRI to assess for any changes in the Medial Temporal lobe and for any incidence of vasogenic edema and microhemorrhage.

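### Two MMSE totals are taken before the first dose, but the cognitive plan names no baseline-adjusted model and gives the screening score no role beyond entry

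*Combined protocol and SAP*

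**What the plan says.** - **Study Events, screening:** "At the initial visit (screen), after informed consent is obtained, the MMSE is performed". The score is checked against the entry range of 10 to 26 in the inclusion criteria. No other use is stated.
- **Study Events, Day 1:** "they will return for their baseline Day 1 (randomization) visit", and "This visit takes place about 1 to 4 weeks after the screen visit". At that visit "tests of cognition, such as the MMSE, ADAS-cog, the ADCS-ADL scale, Trails A, Trails B, CDR, and the Mohs Cancellation task, are administered"; delivery of the test article is described after the tests. The Study Schedule marks the MMSE at screening, Day 1, Day 15 and both follow-ups.
- **Specific Aim 2**, the aim that covers the MMSE: "A battery of cognitive tests will be performed at baseline and at approximately 15, 45, and 90 days after initiation". It does not define baseline further. The fuller label is in Exploratory Aim 1 ("A battery of cognitive tests will be performed at baseline Day 1 and at approximately 15, 45, and 90 days after initiation"), whose listed tests do not include the MMSE.
- **Data Analysis Plan, Secondary Endpoint:** the lead cognitive measures are the "MMSE total score and ADAS-cog total scores". The section specifies standard scoring and a Bonferroni correction over tests and time points. It names no change score, covariate or model. The Important Note at the end of the plan adds independent t-tests as something that may be used.

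**The concern.** With 20 participants per arm, a power table built on alpha 0.20 and power 0.60, and a Bonferroni correction on top, the cognitive comparison is short of precision. A pre-dose score is the cheapest source of it, because it explains part of the spread between people at follow-up. Here two such scores exist on a lead measure, and the plan commits to using neither in the comparison. If the optional t-test is run on follow-up scores, both are left out. If the analyst takes the Day 1 visit label as the analysis baseline, the screening score is left out.

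Both scores precede the first dose. The entry gate, regression to the mean and practice effects therefore act on both arms alike, and adjusting for both scores does not bias the arm comparison. What is at stake is precision, not validity.

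**Working it through.** **1. The plan's own figure.** Sample size considerations gives 20 per group for effect size 0.5, two-tailed, alpha 0.20, power 0.60. The noncentral t gives power 0.613 at 20 per group, and 20 is the smallest size that reaches 0.60, so the entry reproduces. Across the table the same method gives 27/53, 10/20, 4/8 and 2/4 (one-/two-tailed) against the stated 27/53, 10/20, 4/8 and 3/4. These are unadjusted two-sample t-tests, so no baseline enters the stated power.

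**2. Formulas.** Set the variance of a follow-up MMSE to 1. Let a be the correlation of screening with Day 1, b of Day 1 with follow-up, and c of screening with follow-up. The documents give none of these, so all are assumptions. Residual variance is:
- unadjusted: 1
- Day 1 as covariate: 1 − b²
- both as covariates: 1 − (b² + c² − 2abc)/(1 − a²)

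**3. Equal correlations (a = b = c = ρ).** The last line becomes 1 − 2ρ²/(1 + ρ).

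| ρ | Day 1 only | Both | Further cut from screening score |
|---|---|---|---|
| 0.5 | 0.750 | 0.667 | 11.1% |
| 0.6 | 0.640 | 0.550 | 14.1% |
| 0.7 | 0.510 | 0.424 | 17.0% |
| 0.8 | 0.360 | 0.289 | 19.8% |
| 0.9 | 0.190 | 0.147 | 22.4% |

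On these figures 20 per arm does the work of 22.5 (ρ = 0.5) to 25.8 (ρ = 0.9) per arm adjusted for Day 1 alone. Simulating selection on a screening score of 10 to 26 (assumed mean 18 to 22, SD 4.5 to 6, ρ 0.7 to 0.9) leaves a cut of about 11 to 20%.

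**4. Screening less correlated with follow-up (a = b = 0.8).** Day 1 alone leaves 1 − 0.64 = 0.36.
- c = 0.75: 1 − (0.64 + 0.5625 − 0.96)/0.36 = 0.326, a cut of 9.3%.
- c = 0.70: 1 − (0.64 + 0.49 − 0.896)/0.36 = 0.350, a cut of 2.8%.
- c = 0.64: 1 − (0.64 + 0.4096 − 0.8192)/0.36 = 0.360, no cut.

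**5. Averaging instead.** With the mean of the two scores as the single covariate, residual variance is 1 − ((b + c)/2)²/((1 + a)/2). For the same three cases:
- c = 0.75: 0.333, a fall of 7.6%.
- c = 0.70: 0.375, a rise of 4.2%.
- c = 0.64: 0.424, a rise of 17.8%.

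**6. Cost of the second covariate.** With 40 participants, the residual degrees of freedom go from 37 to 36, and 37/36 = 1.028, or about 3%. The equal-correlation cuts become about 9% (ρ = 0.5) to 20% (ρ = 0.9). The 2.8% case nets to nothing, and the 0% case to a loss of about 3%.

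**7. Scale in power.** Take ρ = 0.7, effect size 0.5 on the raw SD, 20 per arm and two-sided alpha 0.20, by normal approximation and before any Bonferroni correction or degree-of-freedom cost. Power is 0.618 unadjusted, 0.824 with Day 1, and 0.875 with both. Most of the gain comes from adjusting at all.

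**The case against.** A reader might infer that the plan analyses the MMSE against Day 1 alone. The documents do not say so. Day 1 is labelled baseline as a visit, and in an exploratory aim that does not list the MMSE. The Data Analysis Plan neither uses nor rules out the screening score. This objection stands. The gap is that no baseline-adjusted model is specified, and the screening score is a refinement of that.

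A reader might also take the gain as certain, or expect the mean of the two scores to cut change-score variance by 25% at any correlation. That figure, 2(1 − ρ) against 1.5(1 − ρ), needs all three correlations to be equal. Screening is 1 to 4 weeks further from every follow-up than Day 1 is, so a lower correlation is plausible, and step 5 shows that averaging can then add variance. This stands too, and it rules out averaging as the remedy.

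Against it, a drop to the least favourable values requires fast real change over a gap of at most about four weeks. A model with a drifting true score plus single-visit error, on the protocol's gaps and follow-ups at about 3, 9 and 16 weeks, gives a cut of 3.5 to 22% from two covariates. That assumes reliability of 0.80 to 0.90 and a true-score correlation over 16 weeks of 0.80 to 0.99. It comes to about 1 to 20% after the degree of freedom.

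Finally, the trial is a pilot with a safety primary endpoint, and taking the last pre-dose score as baseline is legitimate practice. Both points are right and limit the weight of this one.

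**Conclusion.** The point holds as a minor improvement in precision. Two pre-dose MMSE totals are collected, no stated analysis uses the screening one beyond eligibility, and no baseline-adjusted cognitive model is named. Relative to adjusting for Day 1 alone, the screening score cuts variance by about 11 to 22% if correlations are equal at 0.5 to 0.9, and by about 0 to 9% in the cases tried where it is less correlated with follow-up. About 3% comes off for the degree of freedom, so the worst case is a small loss. Relative to an unadjusted t-test, adjusting for Day 1 removes ρ² of the variance: 25% at 0.5, 49% at 0.7, 81% at 0.9. All of this rests on assumed correlations.

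It would go too far to call this an error. No stated figure is wrong and the arm comparison is not biased. The gain is confined to one of two lead measures in a secondary endpoint: ADAS-cog has a single pre-dose score, and the safety endpoint is untouched.

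**What to change.** In the Data Analysis Plan, Secondary Endpoint, prespecify that the MMSE comparisons at Day 15 and at the 45- and 90-day follow-ups use ANCOVA, or one repeated-measures model, with Day 1 MMSE and screening MMSE as separate covariates. Do not average the two scores. Keep Day 1 as the labelled baseline, so that the rule under Stopping rules that refers to cognitive decline from baseline keeps its present reading and the protocol does not acquire two MMSE baselines. Settle the wording before treatment codes are opened.

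The cost is one or two sentences and one degree of freedom. It needs no new visit, test or participant, because the screening score is required for entry and the Day 1 score is already scheduled.
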